## Exclusions

Participants will be excluded if they are younger than 18 years old or older than 25 years old, do not complete the survey, or complete the survey implausibly quickly, defined as completing in <1/3 median survey completion time in a soft launch of the survey.

## Sample Size and Power

We used G\*Power 4 to estimate sample size needs to detect an effect of the health, environment, or health + environment messages vs. the control messages using a repeated measures ANOVA examining between-subjects factors. We estimated power assuming an alpha=0.05, correlation among repeated measures of 0.5 (a conservative estimate based on prior studies), and 2 repeated measures (reflecting that participants will rate 2 messages for their

assigned topic in each of the 4 experiments). Under these assumptions, a sample size of 400 participants per experimental arm (1,600 participants total) will yield 90% power to detect a small standardized effect of Cohen's  $f=.10$  (or Cohen's  $d=.20$ ) or larger. To our knowledge, there are not similar studies of dietary substitution messages, so we powered to detect a small standardized effect size. The planned sample size will also yield 90% power to detect effects of Cohen's  $f=.11$  (or  $d=.22$ ) or larger for comparing each intervention topic vs. the other intervention topics, assuming an  $\alpha=0.0167$  (i.e., 0.05 divided by 3, to correct for multiple comparisons).

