## **Statistical Considerations**

### **General Principles**

We will use a two-sided critical alpha of 0.05 to conduct all statistical tests. All confidence intervals presented will be 95% and two-sided. Analyses will include all randomized participants according to experimental conditions they were randomized to (i.e., intent-to-treat). Participants will be prompted to respond to all survey questions before they can continue, so we expect there will be minimal missing data and therefore plan to use complete case analysis.

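### Does calling a correlation of 0.5 conservative, and quoting 90% power for the topic-versus-topic tests, overstate what 400 per arm can detect?

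*Combined protocol and SAP*

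**What the plan says.** The Sample Size and Power section bases the calculation on a "repeated measures ANOVA examining between-subjects factors". The inputs are a significance level ("We estimated power assuming an alpha=0.05"), a "correlation among repeated measures of 0.5 (a conservative estimate based on prior studies"), and "2 repeated measures (reflecting that participants will rate 2 messages for their" assigned topic in each experiment). General Principles makes the tests two-sided: "We will use a two-sided critical alpha of 0.05 to conduct all statistical tests".

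Two power claims follow. For intervention versus control: "Under these assumptions, a sample size of 400 participants per experimental arm (1,600 participants total) will yield 90% power" at Cohen's f = .10 (d = .20). For topic versus topic: "The planned sample size will also yield 90% power to detect effects of" f = .11 (d = .22), at alpha .0167.

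Two other sections bear on the point. Statistical Analyses plans the Bonferroni-Holm procedure over the three topic-versus-topic tests. Exclusions removes participants who "do not complete the survey, or complete the survey implausibly quickly".

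**The concern.** Four things catch the eye.

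- **Direction of the correlation.** In a within-subject comparison a high correlation between repeated ratings helps, so a low assumed value is cautious. Here each participant stays in one arm, and the comparison is between participants. The second rating then adds less information the more it resembles the first, and power falls as the correlation rises. A cautious value is one at or above what earlier studies found. The plan cites two studies but gives no correlation and no range. Two messages on the same topic, rated one after the other on the same four items, could plausibly correlate above 0.5.
- **Thin margin.** At 0.5 the primary power is barely above 90%.
- **Topic-versus-topic figure.** At exactly f = .11 and alpha .0167 the formula gives less than 90%.
- **Denominator.** Neither the synopsis nor the power section says whether 1,600 is counted before or after the exclusions.

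This section is the plan's only statement of which differences the study can detect. If it were too favourable, a null result, above all between two intervention topics, could be read as stronger evidence of no difference than it is.

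**Working it through.** **Inputs from the documents.** 400 per arm, so N = 800 in each two-arm comparison; m = 2 ratings per participant; correlation ρ = 0.5; f = .10 with alpha .05 (primary); f = .11 with alpha .05/3 = .0167 (topic versus topic). For two equal groups, d = 2f.

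**Formula.** For the between-subjects factor, power comes from the noncentral F distribution with

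λ = f² × N × m / (1 + (m − 1)ρ) = f² × 800 × 2 / (1 + ρ), on 1 and 798 degrees of freedom.

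**Step 1: reproduce the primary figure.** λ = 0.01 × 1600 / 1.5 = 10.67. Power is 90.4%, so the stated 90% is right. The two-arm reading is the one that matches: an omnibus test of four arms with N = 1,600 would give 98.2%.

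**Step 2: vary the correlation.** The documents contain only 0.5. Every other value below is an assumption, and 1.0 is a bound, not a scenario.

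| ρ | Primary: f = .10, alpha .05 | Topic versus topic: f = .11, fixed alpha .0167 |
|---|---|---|
| 0.3 | 93.9% | 92.8% |
| 0.4 | 92.2% | 90.6% |
| **0.5 (plan)** | **90.4%** | **88.3%** |
| 0.6 | 88.5% | 86.0% |
| 0.7 | 86.5% | 83.5% |
| 0.8 | 84.6% | 81.0% |
| 1.0 | 80.6% | 76.2% |

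Primary power crosses 90% at ρ of about 0.52. The decline is gradual, roughly two points for each 0.1.

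**Step 3: the topic-versus-topic figure.** λ = 0.0121 × 1600 / 1.5 = 12.91, giving 88.3%. Solving for 90% gives f = .1127, which rounds to the printed .11. The matching d is 2 × .1127 = .225, whereas the printed .22 is twice the rounded f. The gap is a rounding effect in the third decimal of f.

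**Step 4: the procedure that will be used.** The 88.3% holds every comparison to alpha .0167. Under Holm only the smallest of the three p-values faces .0167; the next faces .025 and the last .05. At f = .11 and ρ = 0.5 those levels give 91.1% and 94.8%. Simulating the whole Holm procedure (400 per arm, ρ = 0.5, 400,000 runs) gives, for a d = .22 contrast:

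| Positions of the three topics (SD units) | Power for the d = .22 contrast |
|---|---|
| 0, 0, .22 | about 90.6% |
| 0, .22, .44 (each adjacent pair) | about 94.8% |
| 0, .11, .22 | about 89% |

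The stated 90% is met in the first two patterns and missed by about one point in the third.

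**Step 5: exclusions.** The documents give no loss rate. If 1,600 were counted before exclusions, an assumed 5% loss leaves 380 per arm and primary power of 88.9%; 10% leaves 360 and 87.2%. The topic-versus-topic values at fixed alpha .0167 would be 86.5% and 84.3%. If 400 is the analysed number, which is a natural reading of a power statement, nothing changes.

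**The case for a change.** The case for a change runs as follows. The word chosen carries a claim about direction, and in this design the direction is easy to get wrong. The two cited studies are the only support, and no value from either is shown. The printed d of .22 does not round correctly from .225, and .23 would give 91.2%. The power statement gives its claim at alpha .0167, so that is the level at which to check it, whatever Holm allows later. A few words would settle all of this and the denominator too, at almost no cost.

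Much of that stands as fact. The dependence on ρ is real, the label cannot be checked from the document, and the second digit of d is loose. But an unsupported label is not a wrong one: if the cited studies showed correlations at or below 0.5, the word is accurate, and nothing in the documents says otherwise. The higher correlations that produce lower power are illustrations. The slip in d is a product of rounding f first, and checking at fixed .0167 understates the power of the tests the plan specifies. What remains is a wish for fuller reporting. It does not identify a decision that would come out differently.

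**Conclusion.** No change is needed. The primary 90% is correct under the stated inputs (90.4%). The topic-versus-topic 90% is correct to the two decimals given for f, and about 89% to 95% under the planned Holm procedure. The correlation label is undocumented, but it is not shown to be false. If the true correlation were higher, the cost would be moderate: about two points of primary power at 0.6 and six at 0.8. With 400 analysed per arm, primary power cannot fall below 80.6%.

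This rests on the two-arm reading of the power calculation, equal arms, the d = .20 and .22 targets, and 400 analysed per arm. An assumed 10% loss to exclusions would take primary power to 87.2% at a correlation of 0.5.

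The power paragraph does not enter the analysis. Followed as written, the plan enrols the same participants, fits the same models and reports the same estimates and confidence intervals. Those intervals will reflect the correlation actually observed, and they, rather than the planning figure, show how far a null result can be taken. Quoting the prior correlations and saying that 400 is the analysed count would be tidy, but optional.
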